7.0 RISKS AND DISCOMFORTS

8.0 POTENTIAL BENEFITS

9.0 MONITORING AND QUALITY ASSURANCE

10.0 APENDIX

11.0 REFERENCES

1.0 BACKGROUND AND SIGNIFICANCE

1.1 Historical Background

Hospitals are the standard of care for acute illness in the US, but hospital care is expensive and often unsafe, particularly for older individuals.¹ While admitted, 20% suffer delirium,² over 5% contract hospital-acquired infections,³ and most lose functional status that is never regained.⁴ Timely access to inpatient care is poor: many hospital wards are typically over 100% capacity, and emergency department waits can be protracted. An acute illness that traditionally requires inpatient hospitalization represents a common critical moment in people's lives. Many people worldwide lack access to acute care, some face intense travel burdens to obtain care, while others simply go without. Even those who may receive their care in a hospital will encounter an environment that may be unsafe and expensive. Maintaining high quality acute care facilities in rural areas is a major burden to health care systems.

1.1.1 Previous Clinical studies

We have designed, implemented, evaluated, and continue improving on home-based acute care (e.g., a “home hospital”) for dense urban environments. The home hospital model of care provides in-home acute care to acutely ill patients who would normally be admitted to a traditional hospital. Studies of the home hospital model have demonstrated that a sizeable proportion of acute care can be delivered in the home with equal quality and safety, reduced cost, and improved patient experience.^{5,6} In late 2016, we launched a randomized controlled trial (RCT) of home hospital care, the first RCT to be performed in the US context. With this pilot we showed that hospital-level care could be delivered with similar or better quality and safety but at lower cost.⁷ We subsequently completed a larger RCT that corroborated the pilot’s findings, additionally demonstrating reduced readmissions for those home hospitalized. Since conclusion of this larger RCT, we have enrolled over 500 patients in home hospital care.

1.1.2 Rationale

About 1 in 5 Americans live in rural areas, totaling nearly 60 million people.⁸ Living in a rural area is associated with higher mortality⁹ and poor access to health care, with 23% reporting an average 34-minute drive to their nearest hospital.¹⁰ An acute illness that traditionally requires hospitalization represents a common critical moment in nearly every person’s life. While some in rural areas face intense travel burdens to obtain acute care, others simply go without. Even those who receive care in a hospital may encounter an environment that is unsafe, of poor quality or experience, and expensive.¹¹ This may be particularly true of rural hospitals.^{12,13} In response to this unacceptable geographic disparity, over the last year, our team has designed and refined the rural home hospital (RHH) model through background research, workflow mapping, prototyping, and rapid cycle testing. We conducted a simulation of RHH through a series of “mock admissions” with stable but chronically ill patients in rural Utah. We evaluated the processes, workflows, and technologies involved in RHH and collected qualitative data from the patients, caregivers, and RHH clinical team.

Building on the success of these detailed planning exercises, we propose deploying RHH to care for acutely ill patients in rural and ultra-rural settings in Utah as a proof of concept. This study will evaluate the feasibility and acceptability of the RHH intervention with 3 patients and synthesize key learnings which will be used to refine the RHH model and inform an implementation strategy going forward. If the home hospital model can be successfully deployed in rural and ultra-rural settings, a paradigm shift in access to acute care will occur, providing this care model to rural patients and clinicians.

2.0 SPECIFIC AIMS

2.1 Primary Aim

Assess the feasibility of home hospital care in rural and ultra-rural settings in the United States by deploying a home hospital team to care for acutely ill rural patients at home.

2.2 Secondary Aims

Asses RHH for its acceptability, experience, quality, and safety.

3.0 SUBJECT SELECTION

3.1 Inclusion

Patient inclusion criteria:

Patient clinical inclusion criteria:

- ≥ 18 years old
- Any infectious process (e.g., pneumonia, diverticulitis, cellulitis, complicated urinary tract infection)
- Heart failure exacerbation
- Asthma and chronic obstructive pulmonary disease exacerbation
- Atrial fibrillation with rapid ventricular response
- Diabetes and its complications
- Venous thromboembolism
 - This includes a patient who requires therapeutic anticoagulation and concomitant monitoring (thus requiring inpatient status)
- Gout exacerbation
- Chronic kidney disease with volume overload
- Hypertensive urgency
- End of life / desires only medical management
 - Regarding a patient who desires only medical management, this includes a patient who requires acute care for symptom management but declines any surgical intervention. This may include a patient who is about to transition to hospice care, for example, but still has the functional capacity to meet our criteria below. Under these circumstances, we would make sure that various contingencies, including possible transition to hospice care or hospital readmission, are completely understood by patients and caregivers as applicable.

Patient social inclusion criteria:

- Lives in rural or ultra-rural area (see definitions in Appendix) that can be served by one of our RHH clinicians.
- Has capacity to consent to study
- Can identify a potential caregiver who agrees to stay with patient for first 24 hours of admission. Caregiver must be competent to call care team if a problem is evident to her/him. After 24 hours, this caregiver should be available for as-needed spot checks on the patient.
 - This criterion may be waived for highly competent patients at the patient and clinician's discretion.

Patient caregiver inclusion criteria: (not required for patient participation):

- Age \geq 18 years old
- Has capacity to consent to study
- Lives with or nearby to patient

Clinician inclusion criteria:

- Any member of the rural home hospital (RHH) clinical team (MD, RN, paramedic, NP) who will be participating in the screening and recruitment of patients for the rural home hospital intervention and/or providing care to rural patients that enroll in the intervention.

3.2 Exclusion

Patient exclusion criteria:

Patient exclusion clinical criteria:

- Acute delirium, as determined by the Confusion Assessment Method
- Cannot establish peripheral access (or access requires ultrasound guidance, unless ultrasound guidance is available)
- Secondary condition: active non-melanoma/prostate cancer, end-stage renal disease, acute myocardial infarction, acute cerebral vascular accident, acute hemorrhage
- Primary diagnosis requires controlled substances
- Cannot independently ambulate to bedside commode
- As deemed by on-call MD, patient likely to require any of the following procedures that have not already occurred: computed tomography, magnetic resonance imaging, endoscopic procedure, blood transfusion, cardiac stress test, or surgery
- For pneumonia:
 - Most recent CURB65 > 3 : new confusion, BUN $> 19\text{mg/dL}$, respiratory rate $\geq 30/\text{min}$, systolic blood pressure $< 90\text{mmHg}$, Age ≥ 65 ($< 14\%$ 30-day mortality)¹⁵

- Most recent SMRTCO > 2: systolic blood pressure < 90mmHg (2pts), multilobar CXR involvement (1pt), respiratory rate >= 30/min, heart rate >= 125, new confusion, oxygen saturation <= 90% (<10% chance of intensive respiratory or vasopressor support)¹⁶
 - Absence of clear infiltrate on imaging
 - Cavitary lesion on imaging
 - Pulmonary effusion of unknown etiology
 - O₂ saturation < 90% despite 5L O₂
- For heart failure:
 - Has a left ventricular assist device
 - GWTG-HF¹⁷ (>10% in-hospital mortality) or ADHERE¹⁸ (high risk or intermediate risk 1)*
 - Severe pulmonary hypertension
- For complicated urinary tract infection:
 - Absence of pyuria
 - Most recent qSOFA > 1 (SBP≤100 mmHg, RR≥22, GCS<15 [any AMS]) (if sepsis, >10% mortality)¹⁹
- For other infection
 - Most recent qSOFA > 1 (SBP≤100 mmHg, RR≥22, GCS<15 [any AMS]) (if sepsis, >10% mortality)¹⁹
- For COPD
 - BAP-65 score > 3 (BUN>25, altered mental status, HR>109, age>65) (<13% chance in-hospital mortality): exercise caution
- For asthma
 - Peak expiratory flow < 50% of normal: exercise caution
- For diabetes and its complications
 - Requires IV insulin
- For hypertensive urgency
 - Systolic blood pressure > 190 mmHg
 - Evidence of end-organ damage; for example, acute kidney injury, focal neurologic deficits, myocardial infarction
- For atrial fibrillation with rapid ventricular response
 - Likely to require cardioversion
 - New atrial fibrillation with rapid ventricular response
 - Unstable blood pressure, respiratory rate, or oxygenation
 - Despite IV beta and/or calcium channel blockade in the emergency department, HR remains > 125 and SBP remains different than baseline
 - Less than 1 hour of time has elapsed with HR < 125 and SBP similar or higher than baseline
- For patients with end-stage renal disease on peritoneal dialysis
 - Peritoneal catheter malfunction
 - Requires temporary hemodialysis
- Home hospital census is full (maximum 3 patients at any time)

*GWTG-HF: AHA Get with the Guidelines: SBP, BUN, Na, Age, HR, Black race, COPD
ADHERE: Acute decompensated heart failure national registry: BUN, creatinine, SBP

Patient social exclusion criteria:

- Non-english speaking
- Undomiciled
- No working heat (October-April), no working air conditioning if forecast $> 80^{\circ}\text{F}$ (June-September), or no running water
- On methadone requiring daily pickup of medication
- In police custody
- Resides in facility that provides on-site medical care (e.g., skilled nursing facility)
- Domestic violence screen positive⁸

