3.3 Source of subjects and recruitment methods

All subjects will be associated with the University of Utah Health system. The University of Utah Health has agreed to serve as research collaborator.

A patient may be considered for RHH care if they are acutely ill at home, present acutely ill to a clinic or emergency department, or if they are admitted and require additional days of acute care (“early transfer”):

- If at home: this patient phenotype is well-known to her/his physician and has an acute illness of highly likely etiology (e.g., heart failure or chronic obstructive pulmonary disease exacerbation). The patient’s care team (perhaps primary care or a specialist) will receive a call from the patient describing acute symptoms. The care team will call the RHH nurse practitioner (NP) to describe the case. If appropriate, the RHH NP will call the patient to determine eligibility and interest. If eligible, the RHH MD will make the decision to admit and the MD or NP will consent the patient.
- If presenting acutely ill to a clinic: after appropriate assessment by the clinic care team, and if the team believes the patient requires admission, the clinic care team will call the RHH NP to describe the case. If appropriate, the RHH NP will call the patient to determine eligibility and interest. If eligible, the RHH MD or NP will consent the patient. The patient will be transported home in an appropriate transport (personal car, chair car, or ambulance). The RHH nurse/paramedic will meet the patient in their home.
- If presenting acutely ill to an emergency department: after appropriate assessment by the emergency department team, and if the team believes the patient requires admission, the emergency department care team will call the RHH NP to describe the case. If appropriate, the RHH NP will call the patient to determine eligibility and interest. If eligible, the RHH MD or NP will consent the patient. The patient will be transported home in an appropriate transport (personal car, chair car, or ambulance). The RHH nurse/paramedic will meet the patient in their home.
- If admitted and requiring additional days of acute care (“early transfer”): an ideal patient for this setting is a patient with a heart failure exacerbation requiring additional days of IV diuresis and close monitoring including daily electrolyte and telemetry monitoring. Patients who require additional days of acute care but could be cared for with RHH will

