4.2 Methods of enrollment and procedures for obtaining consent/ informed consent

Clinicians:

- If the clinician meets inclusion criteria, then the study team will invite them to participate. The research assistant will explain the purpose of the study, answer initial questions, and seek written informed consent from clinician participants.

Patients:

- If the participant has interest in the program and meets inclusion/exclusion criteria, the MD (either over the phone or via a live video visit) or NP will obtain written informed consent of the participant to enroll in the RHH study.
- The MD will make the final decision to admit the patient to home hospital.

[figure not shown]

Figure 1.

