4.4 Treatment Assignment

All eligible and agreeable patients will be enrolled in RHH.

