5.0 STUDY PROCEDURES

5.1 Study visits and measured parameters

Each day, the RHH clinical team will make in-person and/or virtual visits to the patient's home. These are personnel who have been trained in home health and carry out home health as per the usual care they deliver. The RHH module offers most of the same medical components that are standard of care in an acute care hospital (**Table below**). The typical staff (MD, RN or paramedic), diagnostics (blood tests, vital signs, telemetry), intravenous therapy, and oxygen/nebulizer therapy will all be available for home hospital.

RHH improves upon the components of a typical ward's standard of care in several ways:

- Point of care blood diagnostics (results at the bedside in <5 minutes);
- Minimally invasive continuous vital signs, telemetry, and activity tracking
- 24/7 clinician video visits;
- Ambulatory/portable infusion pumps that can be worn on the hip;

Component	Module		
Personnel	  Nurse/Paramedic 
 • 2 daily visits (1 in-person; 1 virtual) • Medication administration • IV access management • Education 		 Physician 
 • 1 daily interaction • Medical decision making
Diagnostics	Point of care: BMP, Hgb/Hct, PT/INR, ultrasound, x-ray, PFTs, ECG		
Pharmacy	Any inpatient medication, most any route		
Equipment	Ambulatory infusion pump, peripheral IV, oxygen concentrator		
Communication	Telepresence/virtual visits		
Monitoring	Wireless remote vital signs, telemetry, activity tracking		

Table 1.

As denoted in the table above, the physician will make at least one daily virtual visit to the patient's home, facilitated by the nurse/paramedic. At the discretion of the physician and nurse/paramedic, the physician can make additional virtual visits should the patient's clinical condition require it. Similarly, the nurse/paramedic will make at least two daily visits to the patient's home. At the discretion of the physician and nurse/paramedic, the nurse/paramedic can make additional visits should the patient's clinical condition require it. This will be an ongoing twice daily discussion among clinicians, patient, and caregivers, as applicable. A patient or clinician can initiate a video visit at any time. As denoted in the table above, the RHH team uses a suite of communication software to communicate with the patient and among team members.

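### Could a failed IV attempt at home be recorded as ineligibility and so drop out of the primary feasibility endpoint?

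*Combined protocol and SAP*

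**What the plan says.** The exclusion in section 3.2 reads "Cannot establish peripheral access (or access requires ultrasound guidance, unless ultrasound guidance is available". It names no time point, operator or number of attempts.

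Section 3.3 gives four entry routes. For a patient at home the nurse practitioner screens by telephone: "If appropriate, the RHH NP will call the patient to determine eligibility and interest". The next step is "If eligible, the RHH MD will make the decision to admit and the MD or NP will consent the patient". Section 4.1 has the physician check the clinical and social criteria further. Section 4.2 then has written consent taken by the nurse practitioner or by the physician, the latter "either over the phone or via a live video visit". Section 4.4 adds: "All eligible and agreeable patients will be enrolled in RHH".

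In section 5.1, Table 1 gives the nurse or paramedic "IV access management" and lists as equipment "Ambulatory infusion pump, peripheral IV, oxygen concentrator". Ultrasound appears among the diagnostics: "Point of care: BMP, Hgb/Hct, PT/INR, ultrasound, x-ray, PFTs, ECG". The Figure 2 caption puts deployment to the home after triage.

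The primary endpoint (section 5.5.1) is whether the admission, daily-care and discharge processes were carried out. Its sources are a process checklist, which is an attachment, and clinician interviews. Section 6.1 plans 3 patients, individual data points or medians with interquartile ranges, and no formal testing.

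**The concern.** Difficult veins can be asked about on the telephone, but inability to place a line is shown only by trying. On the at-home route no one from RHH is described as being with the patient until the nurse or paramedic arrives. The exclusion can therefore turn on what the RHH team manages at its first visit, and its own wording depends on whether ultrasound guidance is to hand, which is a matter of resources.

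That overlaps with the primary endpoint. If a failed attempt made the patient ineligible, and only eligible patients are enrolled, that patient would fall outside the 3. The access step would then succeed by construction among those who count, and a feasibility study would lose a case in which home delivery failed. Listing individual data would not repair this, because the patient would not be in the listing.

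**Working it through.** The plan has no sample-size calculation, error rate or target proportion to reproduce. The check is the order of events, followed by an illustration of size.

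**Order on the at-home route**

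1. Eligibility is judged by telephone (3.3), with the physician's further check of the criteria (4.1).
2. The physician decides to admit, and consent is taken (3.3, 4.2).
3. The eligible, consenting patient is enrolled (4.4).
4. The nurse or paramedic deploys to the home (5.1, Figure 2 caption).
5. Any attempt at a line by RHH comes at step 4 or later.

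So when RHH first tries for access, the patient has passed steps 1 to 3. No section re-applies the exclusions after enrolment or turns an enrolled patient into an ineligible one. What the plan does provide for is an admission process not accomplished (5.5.1), escalation to hospital as a secondary endpoint (5.5.2), and transfer with withdrawal (5.6). Withdrawal presupposes enrolment.

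**Is line placement an admission item?** Table 1 makes access management an RHH task. The deployment steps in the Figure 2 caption are a remote physician evaluation, welcome and education, and set-up of monitoring and communication. Line placement is not among them. Whether it is scored depends on the process checklist, which was not available.

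**Size if the patient were nevertheless reclassified** (one failure; exact Clopper-Pearson 95% intervals)

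| Handling | Result | 95% interval |
|---|---|---|
| Counted, enrolment stops at 3 | 2/3 = 67% | 9% to 99% |
| Counted, one more enrolled | 3/4 = 75% | 19% to 99% |
| Dropped, not replaced | 2/2 = 100% | 16% to 100% |
| Dropped, replaced | 3/3 = 100% | 29% to 100% |

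When all n succeed, the lower limit is 0.025^(1/n): 0.025^(1/2) = 0.158 and 0.025^(1/3) = 0.292.

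**Chance that the case arises.** The documents give no failure rate, so p is an assumption. With k patients entering from home, P(at least one failure) = 1 − (1 − p)^k.

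| p (assumed) | k = 1 | k = 2 | k = 3 |
|---|---|---|---|
| 5% | 5% | 10% | 14% |
| 10% | 10% | 19% | 27% |
| 20% | 20% | 36% | 49% |

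For example, 1 − 0.8³ = 1 − 0.512 = 0.488. With k = 0 the chance is zero. The percentages and intervals in both tables are illustrations; the plan contains no such analysis.

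**The case for a change.** The case for a change is that the natural reading is not written down. The text does not say when eligibility closes, what happens to a patient found after consent to meet an exclusion, which patients form the denominator of the primary endpoint, or whether a withdrawn patient is replaced to reach 3. Section 5.6 withdraws subjects in problematic situations without saying whether they still count. Delirium by the Confusion Assessment Method and the scores that use blood urea nitrogen raise the same timing question at home, but they describe the patient's condition. Failed access can describe the team's performance, so it comes closest to the endpoint. With 3 patients, one classification matters more, and a sentence would cost little.

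The silence is real, and that part stands. It does not show that the plan misdirects anyone: the opposite classification needs a retroactive rule that the documents do not contain. Nor would a failed attempt easily vanish. Clinician interviews are a source for the primary endpoint, and clinicians are consented participants in their own right (4.2), so their account does not depend on one patient's status. Quality and safety data are reviewed daily and weekly (9.0). The at-home route is for patients well known to their physician (3.3), so known access difficulty can be raised before consent. On the other three routes a clinical team has seen the patient in person first, although the text does not say that a line is already in place.

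**Conclusion.** No change is needed. Followed in its written order, the plan places a failed access attempt on a patient already judged eligible, admitted and enrolled. It would most naturally be recorded as a process not accomplished or an escalation, and shown among the individual data. The missing counting rule is a detail that analysts of a 3-patient descriptive study would settle in that way.

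If someone did drop and replace such a patient, 2/3 would read as 3/3. No threshold, test or stated decision depends on that figure, and the intervals (9% to 99% and 29% to 100%) overlap over most of their range. Under assumed failure rates of 5% to 20%, the situation arises with probability 5% to 20% if one patient enters from home, 14% to 49% if all three do, and never if none does.

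This rests on the sequence in sections 3.3 and 4.1 to 4.4 being followed as written, and on the unseen process and eligibility checklists not re-applying the exclusion after consent.

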3.3 Source of subjects and recruitment methods

All subjects will be associated with the University of Utah Health system. The University of Utah Health has agreed to serve as research collaborator.

A patient may be considered for RHH care if they are acutely ill at home, present acutely ill to a clinic or emergency department, or if they are admitted and require additional days of acute care (“early transfer”):

- If at home: this patient phenotype is well-known to her/his physician and has an acute illness of highly likely etiology (e.g., heart failure or chronic obstructive pulmonary disease exacerbation). The patient’s care team (perhaps primary care or a specialist) will receive a call from the patient describing acute symptoms. The care team will call the RHH nurse practitioner (NP) to describe the case. If appropriate, the RHH NP will call the patient to determine eligibility and interest. If eligible, the RHH MD will make the decision to admit and the MD or NP will consent the patient.
- If presenting acutely ill to a clinic: after appropriate assessment by the clinic care team, and if the team believes the patient requires admission, the clinic care team will call the RHH NP to describe the case. If appropriate, the RHH NP will call the patient to determine eligibility and interest. If eligible, the RHH MD or NP will consent the patient. The patient will be transported home in an appropriate transport (personal car, chair car, or ambulance). The RHH nurse/paramedic will meet the patient in their home.
- If presenting acutely ill to an emergency department: after appropriate assessment by the emergency department team, and if the team believes the patient requires admission, the emergency department care team will call the RHH NP to describe the case. If appropriate, the RHH NP will call the patient to determine eligibility and interest. If eligible, the RHH MD or NP will consent the patient. The patient will be transported home in an appropriate transport (personal car, chair car, or ambulance). The RHH nurse/paramedic will meet the patient in their home.
- If admitted and requiring additional days of acute care (“early transfer”): an ideal patient for this setting is a patient with a heart failure exacerbation requiring additional days of IV diuresis and close monitoring including daily electrolyte and telemetry monitoring. Patients who require additional days of acute care but could be cared for with RHH will

be approached for enrollment after discussion with the RHH NP, RHH MD, and hospital care team, ensuring it is an appropriate time to approach for enrollment. If the patient and all stakeholders are in agreement with RHH, the patient will be enrolled and consented to RHH by the RHH MD or NP. The patient will be transported home in an appropriate transport (personal car, chair car, or ambulance). The RHH nurse/paramedic will meet the patient in their home.

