4.0 SUBJECT ENROLLMENT

4.1 Screening and recruitment

Patients:

- Acutely ill patient is screened and recruited as above.
- If participant agrees, the RHH MD will further describe the program, answer initial questions, and further assess whether the participant meets inclusion/exclusion non-clinical (e.g., social) and clinical criteria (please see the subject eligibility checklist)

Clinicians

- Members of the rural home hospital clinical team (MD, RN, paramedic, NP) that have expressed interest in participating in research activities and meet inclusion criteria will be approached by a member of the study team.

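### Does the at-home entry route let a heart failure patient in without the blood results that the exclusion needs?

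*Combined protocol and SAP*

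**What the plan says.** Section 3.3 describes four ways in. Three of them start with the patient already seen: the clinic route proceeds "after appropriate assessment by the clinic care team", the emergency department route is worded alike, and early-transfer patients are already inpatients. The at-home route starts with phone calls (patient to care team, care team to nurse practitioner, nurse practitioner to patient) and continues: "the RHH NP will call the patient to determine eligibility and interest. If eligible, the RHH MD will make the decision to admit". It is limited to cases where "this patient phenotype is well-known to her/his physician" and the cause is not in much doubt. Heart failure and COPD are its examples.

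The heart failure exclusion in 3.2 is a risk class on either of two scores (">10% in-hospital mortality) or ADHERE"). The footnote to 3.2 lists their components: "GWTG-HF: AHA Get with the Guidelines: SBP, BUN, Na, Age, HR, Black race, COPD" and "ADHERE: Acute decompensated heart failure national registry: BUN, creatinine, SBP".

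Section 4.1 then has the physician "further assess whether the participant meets inclusion/exclusion non-clinical (e.g., social) and clinical criteria (please see the subject eligibility checklist"). Section 4.2 makes consent depend on meeting the criteria and gives the physician the final say on admission. Table 1 in 5.1 lists a point-of-care BMP, and the Figure 2 legend puts a remote medical evaluation at the first home visit.

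On renal disease, 3.2 lists end-stage renal disease among excluding secondary conditions. Later it gives two exclusions specific to such patients on peritoneal dialysis: catheter malfunction and need for temporary hemodialysis.

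**The concern.** On a plain reading of 3.3, eligibility on the at-home route is settled by telephone, yet a phone call cannot yield BUN, sodium or creatinine. The pneumonia and infection scores in 3.2 ask for the most recent value; the heart failure scores do not, so it is unclear whether results on file would do or how old they may be. Another general exclusion, "Cannot establish peripheral access", cannot be settled by phone either. If a patient were admitted first and found ineligible at the first home visit, the return to hospital might be counted as an escalation of home hospital care when it was really a screening miss. With 3 patients, one such case is a third of the sample, and the admission process is itself part of the primary feasibility endpoint in 5.5.1.

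The renal entries raise a separate worry. If end-stage renal disease already excludes, the peritoneal dialysis lines seem to have no purpose unless some of those patients may enrol, and two screeners could then treat the same candidate differently.

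**Working it through.** The plan has no figure to reproduce: 6.1 gives 3 patients, individual data points or medians with interquartile ranges, and no testing. The check is a count of score inputs followed by a reading of the sections together.

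**Score inputs (footnote to 3.2)**

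| Score | Blood | Vital signs | History | Total |
|---|---|---|---|---|
| GWTG-HF | BUN, Na | SBP, HR | age, race, COPD | 7 |
| ADHERE | BUN, creatinine | SBP | none | 3 |
| Distinct, both | 3 | 2 | 3 | 7 + 3 − 2 shared (BUN, SBP) = 8 |

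What each source can supply:
- Phone history alone: 3 of 8.
- Plus self-measured vital signs (assumption): 3 + 2 = 5 of 8.
- Plus results on file, or a BMP with vital signs taken at a home visit: 5 + 3 = 8 of 8. This assumes that the panel contains all three blood values, since the protocol does not list its contents.

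So neither score can be completed from the call alone. No score cut-points are given, so how often the missing values would decide the exclusion cannot be computed.

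**Does the plan enrol an unscored patient?**
1. Section 3.3 has the nurse practitioner screen by phone.
2. Section 4.1 has the physician check the clinical criteria further, with a checklist.
3. Section 4.2 allows consent only if the criteria are met.
4. Nothing in 3.3 or 4.1 waives the heart failure criterion on this route.

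Followed as written, these steps keep the exclusion in force. The text does not fix whether step 2 comes before or after the first home visit. If before, earlier results are needed; if at the visit, the point-of-care panel is available. It therefore does not follow that only patients with earlier results can be scored. None of the four routes names a blood test as an eligibility step, so the silence is how 3.3 is written throughout and is not peculiar to the at-home route.

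**Order of consent and admission**
Section 3.3 mentions the decision to admit and then consent, joined in one sentence. Section 4.2 gives consent in one bullet and, in the next, says who decides. Neither uses words of sequence, so listing order alone is not a contradiction.

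**Renal entries**
Two yes/no items give 2² = 4 patterns among peritoneal dialysis candidates.
- Renal disease secondary: the general line excludes all 4. The dialysis lines exclude the 3 with at least one item present and are silent on the 1 with neither. That one pattern is where the tension lies.
- Renal disease primary: the general line, confined to secondary conditions, does not apply. The dialysis lines act alone and exclude 3 of 4.

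The second case gives the dialysis lines a purpose without contradicting the general line. Section 3.1 admits chronic kidney disease with volume overload, which makes that reading plausible, though 3.1 does not name end-stage disease. These are patterns, not frequencies.

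**Effect on results**
One patient relabelled moves a proportion by 1/3 = 33.3 percentage points, but 6.1 does not plan to report a proportion. Section 9.0 sends each transfer back to hospital for review of attribution, and 5.5.1 and 6.2 add clinician interviews. The reason for any return would be visible case by case.

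**The case for a change.** The best case for a change is that the admission workflow is what this study tests. Its lessons are meant to refine the model, so a route whose eligibility step is unspecified weakens the feasibility result itself. Both examples on the route raise the question, since the COPD entry in 3.2 also uses a score with BUN, although that entry is marked as a caution. The remedy would be cheap: some wording and one reporting category, using equipment already listed.

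Part of this stands. The available text does not state the source, timing or permitted age of the blood values, and 3.2 does not say how its two renal entries relate. A sentence on each would be harmless housekeeping; on the renal entries, which reading is meant is for the sponsor's clinicians to say.

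The rest does not carry. Whether the primary endpoint separates a screening miss from other failures cannot be judged, because its data source is a process checklist outside the available text. A category that took such a patient out of the escalation count in 5.5.2 would remove a real return to hospital from a safety-related outcome, which is worse than recording the return with its reason. Asking for source, timing and maximum age in 3.3 is a request for screening procedure, which normally sits in the eligibility checklist that 4.1 cites.

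**Conclusion.** No change to the plan follows. The at-home text leaves an operational gap that the physician's check in 4.1, the consent condition in 4.2 and the panel in Table 1 allow staff to fill sensibly. The renal wording is an ambiguity by implication, limited to peritoneal dialysis candidates with neither listed problem whose renal disease is secondary.

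Size: 3 of 8 score inputs need blood; between 0 and 3 of the 3 patients may use the route, since its use is not stated; no planned figure or conclusion is shown to move.

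This rests on two assumptions: that the physician's check is carried out as 4.1 and 4.2 describe, and that outcomes are reported patient by patient, as 6.1 permits. If the eligibility checklist or Figure 1 names the source of the blood results, the first query disappears altogether.
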